3.2. Scientific Rationale for Study Design

The single age cohort in this Phase 2/3 study, 12 to < 18 years of age, was established to understand the tolerability and immunogenicity of 100 µg (Part 1A) and 50 µg (Part 1C-1, Part 1C-2, and Part 2) mRNA-1273, as well as 50 µg (Part 3) mRNA-1273.222 in an adolescent population. The lower age boundary used in this study is consistent with the definition of adolescence provided by the American Academy of Pediatrics (Hardin et al 2017).

With SARS-CoV-2 expected to be circulating in the general population during the study, all participants will provide preinjection blood samples and postinjection blood samples for Ab analysis through 12 months after the last dose of IP during Part 1A, Part 2, and through 6 months (for participants who receive Dose 2) or 1 to 6 months after the last dose of IP in Part 3 of the study. In addition, participants will have NP or nasal swab samples collected before the injection on Day 1 (Part 1A, Part 1C, Part 2, and Part 3), Day 29 (Part 1A, Part 2, and Part 3), Day 149 (Part 2 participants who receive the booster dose), and Day 181 (Part 3 participants who receive Dose 2); additional timepoints are in the SoA (Table 10 and Table 12 through Table 18). Furthermore, with any signs or symptoms or MAAE suggesting SARS-CoV-2 infection in a participant, an additional nasal or NP swab sample and a blood sample will be taken to confirm the diagnosis of SARS-CoV-2 via serology and RT-PCR. Additionally, clinical information will be carefully collected to evaluate the severity of the clinical case.

As it is possible that participants are naturally exposed to SARS-CoV-2 through community exposure, the NP or nasal swab samples collected before study injection and the serologic assays for Ab responses to nonvaccine antigen(s) may help discriminate between natural infection and vaccine-induced Ab responses, should such discrimination be needed.

Part 1B, is the Open-label Observational Phase. During Part 1B of the study, all ongoing study participants were permitted (a) to be informed of the availability and eligibility criteria of any COVID-19 vaccine made available under an EUA and (b) to schedule a study visit to know their original group assignment (placebo vs. mRNA-1273 vaccine). Part 1B also provided the opportunity for eligible study participants who previously received placebo to receive 2 doses of mRNA-1273 vaccine under open-label conditions.

Part 1C, the Booster Phase and Part 2, were prompted by the recent interim results of an ongoing Moderna Phase 2 study (mRNA-1273-P201). In Part A of Study mRNA-1273-P201, the time course and magnitude of antibody (both bAb and nAb) responses to mRNA-1273 was similar between 100 µg and 50 µg dose levels (both showing strong immunogenicity) at each postbaseline timepoint (Days 29, 43, 57, and 209), although the 100 µg dose group had numerically greater responses. In Part B of Study mRNA-1273-P201 in which participants who had received 2 doses of 50 µg or 100 µg of mRNA-1273 6-8 months prior were administered a 50 µg booster of mRNA-1273, participants demonstrated enhanced immune responses compared to preboost levels and met the noninferiority criteria stipulated in the FDA Guidance on EUA for Vaccines to Prevent COVID-19. In addition, interim results from Study mRNA-1273-P205 show that a 50 µg booster of mRNA-1273 increased nAb levels against Omicron approximately 37-fold compared to preboost levels. No new safety signals emerged upon administration of the BD in Study mRNA-1273-P201. Available data (DMID 21-0012) also show that heterologous or mixed series of COVID-19 vaccine-induced strong immune response in the adult population with persons who received an mRNA-based booster vaccination achieving a four-fold increase in their neutralization response more frequently than those who were boosted with Ad26.COV.S. (Atmar et al 2021).

Part 3 was prompted by preclinical data on bivalent vaccine (mRNA-1273.214 given as 2 dose primary series) showing broader neutralization across divergent lineages. Preclinical mice studies also show increased immunogenicity after BD of the BA.1 & BA.4/BA.5 Omicron Bivalent Vaccines (mRNA-1273.214 & mRNA-1273.222). Further, mRNA-1273.214 when given as 50 µg BD in Study P205 participants elicited superior nAb responses against the Omicron subvariants BA.4, BA.5 compared with mRNA-1273 50 µg (nominal α of 0.05) and the BA.4, BA.5. nAb response was consistently higher in the mRNA-1273.214 group compared to the mRNA-1273 group in participants with and without prior SARS-CoV-2 infection (although higher GMT titers post BD were observed in those who were SARS-CoV-2 positive at pre-BD). Data also demonstrate antibody responses 180 days after the 50 µg mRNA-1273.211 BD were higher than those after a 50 µg mRNA-1273 BD (NCT04405076; Chalkias et al 2022a) against the ancestral SARS-CoV-2 and Beta, as well as Omicron BA.1 and Delta variants. In addition, the bivalent Omicron BA.4/BA.5-containing vaccine mRNA-1273.222 elicited superior neutralizing antibody responses against BA.4/BA.5 compared to mRNA-1273, with no safety concerns identified (Chalkias et al 2022c). Given the increasing prevalence of SARS-CoV-2 infection in the community (Clarke et al 2022), effectiveness of 50 µg mRNA-1273.222 post dose 1 will be evaluated as a primary objective under Part 3. Recent IA results from Study P203 Part 2 also support evaluation of immunogenicity of a single 50 µg-dose. Study P203 Part 2

interim results show higher immunogenicity post dose 1 of 50 µg mRNA-1273 in Study P203 unvaccinated baseline SARS-CoV-2 positive adolescent participants when compared to immunogenicity post primary series in unvaccinated baseline SARS-CoV-2 negative young adults in Study P301 (GMR of 4.322 [95% CI: 3.274, 5.707]). An IA conducted for Part 3 demonstrate robust immunogenicity of a single 50 µg mRNA-1273.222 dose. The pre-specified co-primary endpoints were also met allowing inference of vaccine effectiveness of a single dose from the pivotal Study P301. The study vaccine was also well-tolerated after a median of ~1 month after Dose 1. Based on these results, the second dose of mRNA-1273.222 in Part 3 was removed.

Based on cumulative evidence, the benefit-risk profile of monovalent mRNA-1273 and bivalent mRNA-1273.222 vaccine is favorable, particularly in light of increasing breakthrough disease with the emergence of the Delta and Omicron variants.

3.3. Justification for Dose, Control Product, and Choice of Study Population

The 100 µg dose level is currently being investigated in a large Phase 3 efficacy study in adults 18 years of age and older; therefore, based on this and the results of the studies described in [Section 1.2.2](#), the Sponsor intended to study a single dose level of 100 µg in Part 1A of this Phase 2/3 study in the adolescents age group of 12 to < 18 years of age.

At the time of study initiation, there were no licensed SARS-CoV-2 vaccines available, and so 0.9% sodium chloride was used as a placebo control for the safety and immunogenicity assessments. The mRNA-1273 vaccine and placebo injections look different, so administration was blinded in Part 1A of this study ([Section 8.1](#)).

Interim data from the current Part 1A Study P203 (based on a data snapshot of 08 May 2021) show that the primary immunogenicity objective was met by demonstrating noninferiority of both the (i) GM value of serum nAb and (ii) the seroconversion rate from adolescent participants compared with those from young adults (aged 18 to 25 years) enrolled in the ongoing Phase 3 efficacy study (Study P301).

Following potential EUA of a COVID-19 vaccine for persons under 18 years of age, a study amendment was designed to give EUA-eligible participants the opportunity to transition to Part 1B, the Open-label Observational Phase ([Figure 3](#)). Transitioning the study to Part 1B, open-label Observational Phase, permits (a) all ongoing study participants to be informed of the availability and eligibility criteria of any COVID-19 vaccine made available under an EUA and (b) the option to offer all ongoing study participants who request unblinding an opportunity to schedule a study visit to know their original group assignment (placebo vs. mRNA-1273 [100 µg vaccine]). Part 1B, the Open-label Observational Phase, also provides the opportunity for study participants who previously received placebo to request to receive 2 doses of mRNA-1273 (100 µg) vaccine.

For Part 1C (provision for the option of a single 50 µg BD for eligible participants during the Open-Label Observational Phase) and for Part 2 (evaluation of 2 doses of 50 µg given 28 days apart), the selected 50 µg dose was based primarily on data from Study mRNA-1273-P201. For Part 1C-2, participants will be boosted at least 3 months post Dose 2. For Part 1C-1, participants are well beyond 3 months post Dose 2 and thus will not be changed to a BD at least 3 months

post Dose 2. In Part A of Study mRNA-1273-P201, the time course and magnitude of antibody (both bAb and nAb) responses to mRNA-1273 was similar between 100 μ g and 50 μ g dose levels (both showing strong immunogenicity) at each postbaseline timepoint (Days 29, 43, 57, and 209), although the 100- μ g dose group had numerically greater responses. In Part B of Study mRNA-1273-P201, administration of a 50 μ g BD of mRNA-1273 6 months or more after the primary series, improved the immune responses to 1.7-fold the peak achieved after the primary vaccination series in the current mRNA-1273-P301 study, where efficacy of mRNA-1273 against COVID-19 was demonstrated. In addition, interim results from Study mRNA-1273-P205 show that 50 μ g booster of mRNA-1273 increased nAb levels against Omicron approximately 37-fold compared to preboost levels.

Available data also show that heterologous or mixed series of COVID-19 vaccine-induced strong immune response in the adult population ([Atmar et al 2021](#)). In a recent DMID study (DMID 21-0012), interim data show Day 15 post-boost neutralization titers ranged from 676.1-901.8 IU50/ml for participants boosted with 100 μ g mRNA-1273 compared to 31.2-382.2 IU50/ml for those boosted with Ad26.COV2.S, and 341.3-677.9 IU50/mL for those boosted with BNT162b2. In general, Day 15 titers post-boost were highest in mRNA-1273-primed participants, followed by BNT162b2 and Ad26.COV2.S, irrespective of the booster vaccine administered ([Atmar et al 2021](#)).

For Part 3, the rationale for assessment of 50 μ g primary series of the bivalent Omicron containing vaccine mRNA-1273.222 is based on the preclinical data on bivalent vaccines given as primary series (mRNA-1273.214) and as BD (mRNA-1273.222) that show robust immunogenicity and broader neutralization across divergent lineages. Clinical data from mRNA-1273.214 bivalent vaccine (given as a 50 μ g BD) also show consistent robust immunogenicity, regardless of SARS-CoV-2 infection status in participants (although higher GMT titers post BD were observed in those who were SARS-CoV-2 positive at pre-BD), with acceptable safety profile. Data also demonstrates antibody responses 180 days after the 50 μ g mRNA-1273.211 BD were higher than those after a 50 μ g mRNA-1273 BD ([NCT04405076](#); [Chalkias et al 2022a](#)) against the ancestral SARS-CoV-2 and Beta, as well as Omicron BA.1 and Delta variants. In addition, the bivalent Omicron BA.4/BA.5-containing vaccine mRNA-1273.222 elicited superior neutralizing antibody responses against BA.4/BA.5 compared to mRNA-1273, with no safety concerns identified ([Chalkias et al 2022c](#)).

These data together with increasing prevalence of SARS-CoV-2 infection in the community ([Clarke et al 2022](#)) as well as recent interim results from Study P203 Part 2 showing robust immunogenicity after dose 1 of mRNA-1273 in unvaccinated baseline SARS-CoV-2 positive adolescent participants, prompted the evaluation of the immunogenicity of 2 doses of the bivalent mRNA-1273.222 vaccine given 6 months apart. The 6-month interval will allow evaluation of the immunogenicity of Dose 1. An IA conducted for Part 3 demonstrate robust immunogenicity of a single 50 μ g mRNA-1273.222 dose. The pre-specified co-primary endpoints were also met allowing inference of vaccine effectiveness of a single dose from the pivotal Study P301. The study vaccine was also well-tolerated after a median of ~1 month after Dose 1. Based on these results, the second dose of mRNA-1273.222 in Part 3 was removed.

Taken together, these data strongly suggest that a monovalent 50 μ g mRNA-1273 given as a 2 dose primary series, as a homologous and heterologous booster vaccine is anticipated to provide strong immunogenicity in the adolescent population. Similarly, these data also suggest

that a bivalent 50 µg mRNA-1273.222, given as 1 dose or 2 doses, may provide strong immunogenicity in the adolescent population.

3.4. End-of-Study Definition

The EoS is defined as the date when the last data are available. A participant is considered to have completed the study if the participant has completed all periods of the study including the last visit or the last scheduled procedure as shown in the SoAs.

4. STUDY POPULATION

Participants will be enrolled at approximately 35 to 64 study sites in the USA or out of USA countries.

Prospective approval of protocol deviations to recruitment and enrollment criteria, also known as protocol waivers or exemptions, is not permitted.

4.1. Eligibility Criteria (Part 1A, Part 2, and Part 3)

4.1.1. Inclusion Criteria

Each participant must meet all of the following criteria at the Screening Visit (Day 0) or at Day 1, unless noted otherwise, to be enrolled in this study:

1. Male or female, 12 to < 18 years of age at the time of consent (Screening Visit, Day 0) who, in the opinion of the investigator, is in good general health based on review of medical history and Screening physical examination.
2. Investigator assessment that the participant, in the case of an emancipated minor, or parent(s)/LAR(s) understand and are willing and physically able to comply with protocol-mandated follow-up, including all procedures and provides written informed consent/assent.
3. BMI at or above the third percentile according to WHO Child Growth Standards at the Screening Visit (Day 0); see [Section 10.2.18](#).
4. Female participants of nonchildbearing potential may be enrolled in the study. Nonchildbearing potential is defined as premenarche or surgically sterile (history of bilateral tubal ligation, bilateral oophorectomy, hysterectomy).
5. Female participants of childbearing potential may be enrolled in the study if the participant fulfills all the following criteria:
 - Has a negative pregnancy test at Screening (Day 0), on the day of the first injection (Day 1), and on the day of the second injection (Day 29 in Part 1A and Part 2, and Day 181 in Part 3).
 - Has practiced adequate contraception or has abstained from all activities that could result in pregnancy for at least 28 days prior to the first injection (Day 1).
6. Has agreed to continue adequate contraception or abstinence through 3 months following the second injection (Day 29 in Part 1 A and Part 2, and Day 181 in Part 3).

Adequate female contraception is defined as consistent and correct use of approved contraceptive method in accordance with the product label ([Section 10.3](#)).

4.1.2. Exclusion Criteria

Participants who meet any of the following criteria at the Screening Visit (Day 0) or at Day 1, unless noted otherwise, will be excluded from the study:

1. Has a known history of SARS-CoV-2 infection within 2 weeks prior to administration of IP or known close contact with anyone with laboratory-confirmed SARS-CoV-2 infection

or COVID-19 within 2 weeks prior to administration of IP (Part 2 participants only). For Part 3 participants, known history of SARS-CoV-2 infection within 90 days prior to administration of IP or known close contact with anyone with laboratory-confirmed SARS-CoV-2 infection or COVID-19 within 90 days prior to administration of IP.

2. Travel outside of the USA or home country (Part 2 and Part 3 only) in the 28 days prior to the Screening Visit (Day 0).
3. Pregnant or breastfeeding.
4. Is acutely ill or febrile 24 hours prior to or at the Screening Visit (Day 0). Fever is defined as a body temperature $\geq 38.0^{\circ}\text{C}/\geq 100.4^{\circ}\text{F}$. Participants who meet this criterion may have visits rescheduled within the relevant study visit windows. Afebrile participants with minor illnesses can be enrolled at the discretion of the investigator.
5. Prior administration of an investigational CoV (eg, SARS-CoV-2, SARS-CoV, MERS-CoV) vaccine.
6. Current treatment with investigational agents for prophylaxis against COVID-19.
7. Has a medical, psychiatric, or occupational condition that may pose additional risk as a result of participation, or that could interfere with safety assessments or interpretation of results according to the investigator's judgment.
8. Current use of any inhaled substance (eg, tobacco or cannabis smoke, nicotine vapors).
9. History of chronic smoking (≥ 1 cigarette a day) within 1 year of the Screening Visit (Day 0).
10. History of illegal substance use or alcohol abuse within the past 2 years. This exclusion does not apply to historical cannabis use that was formerly illegal in the participant's state but is legal at the time of Screening.
11. History of a diagnosis or condition that, in the judgment of the investigator, may affect study endpoint assessment or compromise participant safety, specifically:
 - Congenital or acquired immunodeficiency, including HIV infection
 - Suspected active hepatitis
 - Has a bleeding disorder that is considered a contraindication to IM injection or phlebotomy
 - Dermatologic conditions that could affect local solicited AR assessments
 - History of anaphylaxis, urticaria, or other significant AR requiring medical intervention after receipt of a vaccine
 - Diagnosis of malignancy within the previous 10 years (excluding nonmelanoma skin cancer)
 - Febrile seizures

12. Receipt of:

- Any licensed vaccine within 28 days before the first dose of IP or plans for receipt of any licensed vaccine within 28 days before and/or after each dose of IP.
- Systemic immunosuppressants or immune-modifying drugs for > 14 days in total within 6 months prior to the day of enrollment (for corticosteroids, ≥ 20 mg/day prednisone equivalent). Topical tacrolimus is allowed if not used within 14 days prior to the day of enrollment. Participants may have visits rescheduled for enrollment if they no longer meet this criterion within the Screening Visit window. Inhaled, nasal, and topical steroids are allowed.
- Intravenous blood products (red cells, platelets, immunoglobulins) within 3 months prior to enrollment.

13. Has donated ≥ 450 mL of blood products within 28 days prior to the Screening Visit (Day 0) or plans to donate blood products during the study.

14. Participated in an interventional clinical study within 28 days prior to the Screening Visit (Day 0) or plans to do so while participating in this study.

15. Is an immediate family member or has a household contact who is an employee of the research center or otherwise involved with the conduct of the study.

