Interim data from the current Study P203 (based on a data snapshot of 08 May 2021) met the primary immunogenicity objective by demonstrating noninferiority of both the (i) GM value of serum nAb and (ii) the seroconversion rate from adolescent participants compared with those from young adults (aged 18 to 25 years) enrolled in the ongoing Phase 3 efficacy study (Study P301). These interim results supported administration of mRNA-1273 as two 100 µg doses 28 days apart in adolescents between ≥ 12 and 17 years of age. On 17 Jun 2022, the FDA granted EUA of the mRNA-1273 vaccine for adolescents 12 through 17 years of age. Global filings/authorizations down to 12 years of age have also occurred.

An additional objective of the current Study P203 is to evaluate safety and immunogenicity of a 50 µg of mRNA-1273 given as a 2 dose primary series as well as when given as a homologous and heterologous booster vaccine. The rationale for these objectives is as follows: In Part A of Study mRNA-1273-P201 (Study P201), the time course and magnitude of antibody (both bAb and nAb) responses to mRNA-1273 was similar between 100 µg and 50 µg dose levels (both showing strong immunogenicity) at each postbaseline timepoint (Days 29, 43, 57, and 209), although the 100 µg dose group had numerically greater responses. In addition, recent interim results of the ongoing Study P201 support administration of a BD of vaccine. Adult participants in Study P201 received 2 doses of either 50 µg or 100 µg of mRNA-1273 and were administered a 50 µg booster of mRNA-1273 6 to 8 months after the second dose. Participants in Study P201 who received the BD demonstrated enhanced immune responses to SARS-CoV-2 compared to preboost levels and met the noninferiority criteria stipulated in the FDA Guidance on EUA for Vaccines to Prevent COVID-19. Interim results from Study mRNA-1273-P205 (Study P205) also show that a 50 µg booster of mRNA-1273 increased nAb levels against Omicron approximately 37-fold compared to preboost levels. Available data also show that heterologous or mixed series of COVID-19 vaccine-induced high immune response in the adult population ([Atmar et al 2021](#)). Additionally, no new safety signals emerged upon administration of the BD in Study P201. Based on cumulative evidence, the benefit-risk profile of a BD of mRNA-1273 is favorable, particularly in light of increasing breakthrough disease with the emergence of the Delta and Omicron variants.

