The Sponsor also aims to evaluate the safety and immunogenicity of a 50 µg of mRNA-1273.222 given as a 2 dose primary series in COVID-19 vaccine-naïve participants. Evaluation of the immunogenicity of 2 doses of the bivalent mRNA-1273.222 vaccine given 6 months apart which allows evaluation of immunogenicity post Dose 1 was prompted by following emerging data: a) Recent disease trends support the need for pediatric vaccination strategies that induce broader protection against VOCs (eg, Omicron variant) in addition to the ancestral SARS-CoV-2 strain, b) increasing prevalence of SARS-CoV-2 infection in the community ([Clarke et al 2022](#)), c) Study P205 data show that Omicron containing vaccine (ie, mRNA-1273.214) elicits strong immunogenicity in SARS-CoV-2 positive individuals ([Chalkias et al 2022b](#)), and d) durability of immune response post BD of a bivalent Beta containing vaccine (mRNA-1273.211) up to 6 months with higher nAb responses in adults compared with mRNA-1273 against D614G, Beta, Omicron BA.1, and Delta variants ([Chalkias et al 2022a](#)). Results of Part 3 IA demonstrate robust immunogenicity of a single 50 µg mRNA-1273.222 dose. The pre-specified co-primary endpoints were also achieved, allowing inference of vaccine effectiveness of a single dose from the pivotal Study P301. Based on these results, Protocol Amendment 7 was initiated to remove Dose 2 administration of mRNA-1273.222 from Part 3.

The Sponsor has developed mRNA-1273.222, a bivalent vaccine consisting of the mRNA that encodes for the prefusion stabilized spike glycoprotein of both the Wuhan-Hu-1 isolate of SARS-CoV-2 and the SARS-CoV-2 B.1.1.529, Omicron, variant. In November 2021, the SARS-CoV-2 Omicron variant was detected in South Africa and was found to contain potential antibody escape site mutations such as K417N, T478K, E484A, and N501Y.

The ability of the Omicron variant to escape prior immunity led to an unprecedented rise in COVID-19 infections and related hospitalizations, in adults as well as children, between December 2021 and February 2022. Real world effectiveness studies in adults conducted during the Omicron wave found a lower efficacy of the prototype vaccine against this new variant

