4.3. Study Eligibility Criteria (Part 1C-1 – Homologous Booster Phase)

Inclusion Criteria:

1. Participants must have been previously enrolled in the mRNA-1273-P203 study, are actively participating in Part 1A or Part 1B and are least 5 months from the last dose.
2. Female participants of childbearing potential may be enrolled in the study if the participant has a negative pregnancy test on the day of the first injection (BD-Day 1).

Exclusion Criteria:

1. Pregnant or breastfeeding.
2. Is acutely ill or febrile 24 hours prior to or at the Screening Visit (Day 0). Fever is defined as a body temperature $\geq 38.0^{\circ}\text{C}/\geq 100.4^{\circ}\text{F}$. Participants who meet this criterion may have visits rescheduled within the relevant study visit windows. Afebrile participants with minor illnesses can be enrolled at the discretion of the investigator.
3. Has a medical, psychiatric, or occupational condition that may pose additional risk as a result of participation, or that could interfere with safety assessments or interpretation of results according to the investigator's judgment.

4. History of a diagnosis or condition (after enrollment in Part 1A) that, in the judgment of the investigator, may affect study endpoint assessment or compromise participant safety:
 - Suspected active hepatitis
 - Has a bleeding disorder that is considered a contraindication to IM injection or phlebotomy
 - Dermatologic conditions that could affect local solicited AR assessments
 - History of anaphylaxis, urticaria, or other significant AR requiring medical intervention after receipt of a vaccine
 - Diagnosis of malignancy (excluding nonmelanoma skin cancer)
5. Receipt of:
 - Any authorized or licensed vaccine within 28 days before the first dose of IP or plans for receipt of any licensed vaccine through 28 days following the last dose of IP (authorized/approved bivalent vaccine against SARS-CoV-2 as 4th BD is not exclusionary); OR
 - Any seasonal influenza vaccine within 14 days before the first dose of IP or plans for receipt of any seasonal influenza vaccine 14 days following the last dose of IP.
6. Participated in an interventional clinical study, other than mRNA-1273-P203, within 28 days prior to the Screening Visit (Day 0) or plans to do so while participating in this study.

4.4. Study Eligibility Criteria (Part 1C-2 – Heterologous Booster Dose):

Inclusion Criteria:

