5.5. Prior and Concomitant Medications

5.5.1. Prior Medications and Therapies

Information about prior medications (including any prescription or over-the-counter medications, vaccines, or blood products) taken by the participant within the 28 days before providing informed consent/assent (or as designated in the inclusion/exclusion requirements) will be recorded in the participant's eCRF.

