The use of the following concomitant medications and/or vaccines will not require withdrawal of the participant from the study (with the exception of planned or actual receipt of a nonstudy COVID-19 vaccine either under EUA or licensed for Part 1A and 1B only) but may determine a participant's eligibility to receive a second dose or evaluability in the PP analysis (analysis sets are described in [Section 8.4](#)):

- Any investigational or nonregistered product (drug or vaccine) other than the IP used during the study period.
- Immunosuppressants or other immune-modifying drugs administered chronically (ie, more than 14 days in total) during the study period. For corticosteroids, this will mean that prednisone ≥ 20 mg/day or the equivalent is not permitted. Inhaled, nasal, and topical steroids are allowed.
- Long-acting immune-modifying drugs administered at any time during the study period (eg, infliximab).
- Immunoglobulins and/or any blood products administered during the study period.

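### Part 3 is described as vaccine-naive, but Section 4.1.2 lets in adolescents who have already had an authorised or licensed COVID-19 vaccine, and nothing in the per-protocol set removes them

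*Protocol*

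**What the plan says.** Section 1.1 gives the Part 3 regimen as 50 µg mRNA-1273.222 "given as a 2 dose primary series in COVID-19 vaccine-naïve participants". Section 3.1.3, after the removal of Dose 2, still calls it a primary series, now of one dose.

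Section 4.1 sets eligibility for Parts 1A, 2 and 3 together. No inclusion criterion mentions vaccination history. Two exclusion criteria in Section 4.1.2 touch on it:

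- Criterion 5: "Prior administration of an investigational CoV (eg, SARS-CoV-2, SARS-CoV, MERS-CoV) vaccine".
- Criterion 12: "Any licensed vaccine within 28 days before the first dose of IP", and planned licensed vaccines within 28 days of a dose.

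Other sections name authorised products separately. The Part 1C-1 criterion in Section 4.3 reads "Any authorized or licensed vaccine within 28 days before the first dose of IP", and Section 5.5.4 refers to a "nonstudy COVID-19 vaccine either under EUA or licensed". Section 1.1 also records that "On 17 Jun 2022, the FDA granted EUA of the mRNA-1273 vaccine for adolescents 12 through 17 years of age". Part 1C-2 (Sections 3.1.1.4 and 4.4) is built on adolescents who completed a non-Moderna series under emergency use authorisation (EUA).

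Section 5.5.1 records prior medications and vaccines "taken by the participant within the 28 days before providing informed consent/assent", or as the eligibility criteria designate. Sections 5.5.2 and 5.5.3 record nonstudy vaccinations from 28 days before the first dose.

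Table 7 (Section 8.4) defines the Part 3 PP Immunogenicity Subset by dose, sampling schedule and absence of major deviations. Baseline status rests on RT-PCR and anti-nucleocapsid serology.

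**The concern.** The Part 3 inference is that one dose, given as a primary series to previously infected adolescents, does at least as well as two 100 µg doses did in the P301 young adults. That reading needs participants whose only earlier exposure was infection. Someone vaccinated before entry gives a booster response. If such people sit in the baseline-positive per-protocol set, both co-primary GMRs are estimated in a mixed population and pulled upward, which is the direction of success. The 4-fold-rise seroresponse rate would tend to move the other way, because earlier vaccination raises the baseline titre.

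The wording appears to be inherited. Section 1.1 says that no vaccine was authorised or licensed when the study began, so the term investigational then covered every SARS-CoV-2 vaccine. It no longer did when Part 3 was added by Amendment 5 (11 Oct 2022).

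**Working it through.** **1. Who can enter under the written criteria**

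| Prior COVID-19 vaccine | Criterion 5 | Criterion 12 | Result |
|---|---|---|---|
| Investigational | excluded | – | out |
| Licensed, within 28 days | not named | excluded | out |
| Licensed, more than 28 days earlier | not named | not reached | eligible |
| Authorised (EUA), any time | not named | not named | eligible |

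The last two rows pass into the per-protocol set if the participant is also baseline positive, since Table 7 adds no vaccination condition.

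**2. The plan's own figures (Section 8.3.3)**

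Inputs: 168 adolescents, 300 young adults, SD 1.5 on the natural log scale, two-sided α 0.05, GMR 1.6 (superiority) and 1.1 (noninferiority, margin 1.5).

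- SE = 1.5 × √(1/168 + 1/300) = 0.1445.
- Superiority: Φ(ln 1.6/0.1445 − 1.96) = 90.2%.
- Noninferiority: Φ((ln 1.1 + ln 1.5)/0.1445 − 1.96) = 93.4%.
- 240 × 0.70 = 168.

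These reproduce the stated power of more than 90% and the stated sample size. A vaccine-naive criterion changes none of them.

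**3. What contamination would do**

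Let a share f of the per-protocol set be previously vaccinated, with titres k times those of the rest. Neither f nor k is in the Protocol; both are assumed. On the log scale the GMR is multiplied by k^f. The chance of passing when the true naive GMR sits exactly on the margin, nominally 2.5%, becomes Φ(f·ln k/0.1445 − 1.96), with the SD held at 1.5. The last two columns divide the reported interim lower bounds in Section 1.2.2.5 (3.693 ancestral, 44.209 BA.4/BA.5) by k^f.

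| f | k | k^f | Pass rate at the margin | Ancestral bound | BA.4/BA.5 bound |
|---|---|---|---|---|---|
| 10% | 1.2 | 1.02 | 3.3% | 3.63 | 43.4 |
| 30% | 1.2 | 1.06 | 5.7% | 3.50 | 41.9 |
| 10% | 2 | 1.07 | 6.9% | 3.45 | 41.2 |
| 30% | 2 | 1.23 | 30% | 3.00 | 35.9 |
| 10% | 5 | 1.18 | 20% | 3.14 | 37.6 |
| 30% | 5 | 1.62 | 92% | 2.28 | 27.3 |
| 50% | 10 | 3.16 | >99% | 1.17 | 14.0 |

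The only hint of k in the Protocol is a cross-part comparison. The Part 1C-1 booster GMR is 5.071 and the Part 3 ancestral GMR is 4.247, a ratio of 1.19. The Part 1C-1 primary analysis set was prebooster negative, so this is indicative only.

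**4. What it would take to reverse the interim result**

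- Ancestral: 3.693/0.667 = 5.5-fold inflation. At f = 50% that needs k = 5.54² ≈ 31.
- BA.4/BA.5: 44.209/1 = 44-fold. At f = 50% that needs k = 44.2² ≈ 1,950.

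**The case against.** **No entry is shown.** No section says that a previously vaccinated adolescent was enrolled. Section 1.1 states the vaccine-naive intent, and Sections 3.2 and 3.3 describe the Part 2 baseline-positive participants as unvaccinated, so the sponsor may have screened for this in practice. That stands: the Protocol permits the entry and does not show that it happened. Sections 4 and 7 prohibit waivers, however, so the written criteria are what sites are held to.

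**Investigational might be read to include EUA products.** Sections 4.3, 4.4 and 5.5.4 name authorised or EUA vaccines separately, which makes that reading hard to sustain.

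**The interim success might seem to be in doubt.** A reader might infer that contamination could have carried an inferior vaccine past the margin. Suppose the naive ancestral GMR were 0.60 and vaccinated participants responded at 5.071. To give the reported 4.247, the vaccinated share would have to be (ln 4.247 − ln 0.60)/(ln 5.071 − ln 0.60) = 92%. Conversely, with vaccinated participants at 5.071, a reported 4.247 implies a naive GMR of 4.06 at 20% contamination and 3.56 at 50%. The Protocol does not support that inference.

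**Prior recipients might seem impossible to identify.** That is too strong. Medical history is taken at Screening (Tables 17 and 18), Section 5.5.1 allows a longer look-back where eligibility designates one, and sites can be queried. What holds is that lifetime COVID-19 vaccination history is not mandated.

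**Part 2 might seem equally affected.** It shares the criteria, but it has no hypothesis test (Section 8.2.2) and enrolment stopped on 16 August 2022. Only its descriptive summaries are touched.

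**Conclusion.** The inconsistency is real and concerns Part 3. The vaccine-naive population of Section 1.1 is not carried into Section 4.1.2, the per-protocol definition, or the required vaccination look-back. Followed as written, the Protocol admits previously vaccinated adolescents to the co-primary analysis.

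The direction of the effect is upward on both GMRs, provided that earlier vaccination raises the post-dose titre. Its size cannot be derived from the Protocol. At modest assumed values (10% to 30% contamination, 1.2-fold to twofold advantage) the inflation is 1.02 to 1.23. With interim lower bounds of 3.693 and 44.209 against criteria of 0.667 and 1, it is unlikely to reverse success.

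Wide margins do not settle who was studied: a high ratio is also what boosted participants would produce. The single-dose, vaccine-naive interpretation already underlies the removal of Dose 2, and it should rest on documented vaccination history rather than on an assumption.

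**What to change.** - **Eligibility.** Reconcile Section 1.1 with Section 4.1.2 by making prior receipt of any COVID-19 vaccine (investigational, authorised or licensed) an exclusion for Part 3.
- **Participants already enrolled.** Query sites for lifetime COVID-19 vaccination history and record it in the eCRF.
- **Analysis.** Exclude any prior recipients from the Part 3 PP Immunogenicity Subset in the final analysis. At the least, report a vaccine-naive sensitivity analysis of both co-primary GMRs.

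The cost is one sentence, one eCRF field, one site query and possibly a few participants lost from the per-protocol set. No stated sample size or power figure changes. If enrolment is already complete, the history query and the analysis condition do most of the work. If no prior recipients are found, the vaccine-naive description is confirmed.
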